1.3 Informed consent

Any incentives for patients who participate in the study as well as any provisions for patients harmed as a consequence of study participation should be described in the informed consent form that is approved by an Ethics Committee.

The Principal Investigator at each centre will:

- Ensure that each patient is given full and adequate oral and written information about the nature, purpose, possible risk and benefit of the study and the optional exploratory biomarker and genetic research components
- Ensure that each patient is notified that they are free to withdraw from the study or the research components at any time
- Ensure that each patient is given the opportunity to ask questions and allowed time to consider the information provided
- Ensure each patient provides signed and dated informed consent before conducting any procedure specifically for the study
- Ensure each original, signed Informed Consent Form is stored in the Investigator's Study File/medical records
- Ensure a copy of each signed Informed Consent Form is given to the patient

The exploratory biomarker and genetic research components of this study are voluntary and the patient may participate in the main study without participating in the exploratory biomarker and/or genetic research parts of the study. To participate in the exploratory biomarker and/or genetic component of the study the patient should sign and date the consent form for the main study and as applicable separate consent forms for the exploratory biomarker and/or the genetic components of the study.

In Japan, if any new information on the study medication becomes available which may influence the decision of the patient to continue the study, the investigator(s) should inform

the patient of such information immediately, record this in a written form, and confirm with the patient if he or she wishes to continue participation in the study. In addition, if the investigator(s) deem it necessary to revise the Informed Consent Form, they should revise it immediately. The investigator(s) should re-explain the information to the patients using the updated Informed Consent Form even though the patients have already been informed of the new information verbally. Written informed consent to continue participation in the study should be provided separately.

1.4 Changes to the protocol and Informed Consent Form

Study procedures will not be changed without the mutual agreement of the Principal Investigator and AstraZeneca.

If there are any substantial changes to the Clinical Study Protocol, then these changes will be documented in a Clinical Study Protocol Amendment and where required in a new version of the protocol (Revised Protocol).

The amendment should be approved by each Ethics Committee and if applicable, also the national regulatory authority, before implementation. Local requirements should be followed for Revised Protocols.

AstraZeneca will distribute any subsequent amendments and new versions of the protocol to each Principal Investigator. For distribution to Ethics Committee see Section 1.2.

If a protocol amendment requires a change to a centre's Informed Consent Form, AstraZeneca and the centre's Ethics Committee should approve the revised Informed Consent Form before the revised form is used.

If local regulations require, any administrative change will be communicated to or approved by each Ethics Committee.

1.5 Audits and inspections

Authorized representatives of AstraZeneca, a regulatory authority, or an Ethics Committee may perform audits or inspections at the centre, including source data verification. The purpose of an audit or inspection is to systematically and independently examine all studyrelated activities and documents, to determine whether these activities were conducted, and data were recorded, analysed, and accurately reported according to the protocol, Good Clinical Practice (GCP), guidelines of the International Conference on Harmonisation (ICH), and any applicable regulatory requirements. The investigator will contact AstraZeneca immediately if contacted by a regulatory agency about an inspection at the centre.

Clinical Study Protocol Appendix E	
Drug Substance	AZD9291
Study Code	D5160C00001
Edition Number	1
Date	

Appendix E Data and Study Management

1. DATA AND STUDY MANAGEMENT

1.1 Patient data protection

The Informed Consent Form will incorporate (or, in some cases, be accompanied by a separate document incorporating) wording that complies with relevant data protection and privacy legislation.

Due to the exploratory nature of the biomarker and genetic research, there will be no routine communication of these results to patients. AstraZeneca will not provide individual results to patients, any insurance company, any employer, their family members, general physician or any other third party, unless required to do so by law.

Extra precautions are taken to preserve confidentiality and prevent genetic data being linked to the identity of the patient. In exceptional circumstances, however, certain individuals might see both the genetic data and the personal identifiers of a patient. For example, in the case of a medical emergency, an AstraZeneca physician or an investigator might know a patient's identity and also have access to his or her genetic data. Also regulatory authorities may require access to the relevant files, though the patient's medical information and the genetic files would remain physically separate.

1.2 Pre-study activities

Before the first patient is entered into the study, it is necessary for a representative of AstraZeneca to visit the investigational study site to:

- Determine the adequacy of the facilities
- Determine availability of appropriate patients for the study
- Discuss with the investigator(s) (and other personnel involved with the study) their responsibilities with regard to protocol adherence, and the responsibilities of AstraZeneca or its representatives. This will be documented in a Clinical Study Agreement between AstraZeneca and the investigator

1.3 Training of study site personnel

Before the first patient is entered into the study, an AstraZeneca representative will visit the study site to review and discuss the requirements of the Clinical Study Protocol and related documents with the investigational staff and also to train them in any study specific procedures including collection of samples and the WBDC system utilised. The additional requirements for the collection of the patients' samples for the exploratory biomarker and genetic research will also be clarified.

The Principal Investigator will ensure that appropriate training relevant to the study is given to all of the staff, and that any new information relevant to the performance of this study is forwarded to the staff involved.

The Principal Investigator will maintain a record of all staff members involved in the study (medical, nursing and other staff).

1.4 Source data

Refer to the Clinical Study Agreement for location of source data.

1.5 Monitoring of the study

During the study, an AstraZeneca representative will have regular contacts with the study sites, including visits to:

- Provide information and support to the investigator(s)
- Confirm that facilities remain acceptable
- Confirm that the investigational team is adhering to the protocol including the specific requirements of the biomarker and genetic research, that data are being accurately and timely recorded in the CRFs, and that investigational product accountability checks are being performed
- Perform source data verification (a comparison of the data in the CRFs with the patient's medical records at the hospital or practice, and other records relevant to the study) including verification of the Informed Consent Form(s)of participating patients. This will require direct access to all original records for each patient (eg, clinic charts)
- If applicable, ensure withdrawal of informed consent to the use of the patient's biological samples is reported and biological samples are identified and disposed of/destroyed accordingly, and the action is documented, and reported to the patient

The AstraZeneca representative will be available between visits if the investigator(s) or other staff at the centre needs information and advice about the study conduct.

1.6 Data management by AstraZeneca

Data management will be performed by the AstraZeneca Data Management Centre.

Data entered in the WBDC system or data captured electronically will be immediately saved to the applicable database and changes tracked to provide an audit trail.

The data collected through third party sources will be obtained and reconciled against study data.

Adverse events and medical/surgical history will be classified according to the terminology of the latest version the Medical Dictionary for Regulatory Activities (MedDRA). Medications will be classified according to the AstraZeneca Drug Dictionary. All coding will be performed by the Medical Coding Team at the AstraZeneca Data Management Centre.

Data queries will be raised for inconsistent, impossible or missing data. All entries to the study database will be available in an audit trail.

The data will be validated as defined in the Data Management Plan. Quality control procedures will be applied to each stage of data handling to ensure that all data are reliable and have been processed correctly.

When all data have been coded, validated, signed and locked, clean file will be declared. Any treatment-revealing data may thereafter be added and the final database will be locked.

Genotype data generated in this study will be stored in the AstraZeneca genotyping Laboratory Information Management System (LIMS) database, or other appropriate secure system, separate from the database used for the main study.

Some or all of the clinical datasets from the main study may be merged with the genetic data in a suitable secure environment separate from the clinical database. The results from this genetic research will be reported separately from the Clinical Study Report for the main study.

1.7 Study agreements

The Principal Investigator at each centre should comply with all the terms, conditions, and obligations of the Clinical Study Agreement, or equivalent, for this study. In the event of any inconsistency between this Clinical Study Protocol and the Clinical Study Agreement, the Clinical Study Protocol shall prevail with respect to the conduct of the study and the treatment of patients and in all other respects, the terms of the Clinical study Agreement shall prevail.

Specific reference to requirements relating to this optional biomarker and genetic research will be included in the study agreement(s).

Agreements between AstraZeneca and the Principal Investigator should be in place before any study-related procedures can take place, or patients be enrolled.

1.7.1 Archiving of study documents

The investigator follows the principles outlined in the Clinical Study Agreement.

1.8 End of study

The end of the study is defined as the last visit of the last patient undergoing the study plus 28days safety follow-up.

The study may be terminated at individual centres if the study procedures are not being performed according to Good Clinical Practice (GCP), or if recruitment is slow. AstraZeneca

Clinical Study Protocol Appendix E Drug Substance AZD9291 Study Code D5160C00001 Edition Number 1 Date

may also terminate the entire study prematurely if concerns for safety arise within this study or in any other study with AZD9291.

Discontinuation or suspension of the whole study programme (Japan)

If AstraZeneca decides to prematurely terminate or suspend the study, the Principal Investigator, Sub-Investigator, the Head of the institution and regulatory authorities should receive written notification of the reasons for the premature termination or suspension.

The Principal Investigator/Sub-Investigator will immediately notify the decision to the patients, give appropriate medical treatment; take necessary measures, and record treatment or measures provided on the source documents.

Completion of the study (Japan)

Upon terminating the study, the Principal Investigator/Sub-Investigator will report in writing the completion of the study as well as the summary of the results to the Head of the study site in accordance with the institution's rules. The Head of the study site who is informed of the termination by the investigator will provide a written notification of the results to the Institutional Review Board and AstraZeneca.

Clinical Study Protocol Appendix F		
Drug Substance	AZD9291	
Study Code	D5160C00001	
Edition Number	1	
Date		

Appendix F Guidelines for Evaluation of Objective Tumour Response Using RECIST 1.1 (Response Evaluation Criteria in Solid Tumours)

1. INTRODUCTION

This appendix details the implementation of RECIST (Response Evaluation Criteria in Solid Tumours) 1.1 guidelines (Eisenhauer et al 2009) for the study with regards to investigator assessment of tumour burden including protocol-specific requirements for this study.

2. DEFINITION OF MEASURABLE, NON-MEASURABLE, TARGET AND NON-TARGET LESIONS

Patients with at least one lesion measurable that can be accurately assessed at baseline by computerised tomography (CT), magnetic resonance imaging (MRI) or plain X-ray should be included in this study.

Measurable lesions

At least one lesion, not previously irradiated, that can be accurately measured at baseline as \geq 10mm in the longest diameter (except lymph nodes which must have short access \geq 15mm) with computered tomography (CT) or magnetic resonance imaging (MRI) which is suitable for accurate repeated measurements.

Non-measurable lesions

- All other lesions, including small lesions (longest diameter < 10 mm or pathological lymph nodes with \geq 10 mm to < 15 mm short axis at baseline. Nodes with < 10 mm short axis are considered non-pathological and should not be recorded as non-target lesions (NTLs)
- Truly non-measurable lesions include the following: bone lesions, leptomeningeal disease, ascites, pleural / pericardial effusion, inflammatory breast disease, lymphangitic involvement of skin or lung, abdominal masses/abdominal organomegaly identified by physical examination that are not measurable by CT or MRI
- Previously irradiated lesions as localised post-radiation changes, which affect lesion sizes, may occur. Therefore, lesions that have been previously irradiated will not be considered measurable and should be selected as NTLs at baseline and followed up as part of the NTL assessment
- Skin lesions assessed by clinical examination
- Brain metastasis

Clinical Study Protocol Appendix F Drug Substance AZD9291 Study Code D5160C00001 Edition Number 1 Date

Special cases

- Lytic bone lesions or mixed lytic–blastic lesions, with identifiable soft tissue components, can be considered measurable if the soft tissue component meets the definition of measurability. Blastic lesions are considered non-measurable.
- Cystic metastases can be considered measurable lesions if they meet the criteria for measurability from a radiological point of view, but if non-cystic lesions are present in the same patient, these non-cystic lesions should be selected as the target lesions (TLs).

Target lesions

A maximum of 5 measurable lesions (with a maximum of 2 lesions per organ), representative of all lesions involved suitable for accurate repeated measurement, should be identified as TLs at baseline.

Non-target lesions

All other lesions (or sites of disease) not recorded as TLs should be identified as NTLs at baseline.

3. METHODS OF MEASUREMENT

The same method of assessment and the same technique should be used to characterise each identified and reported lesion at baseline and during follow-up.

The methods to be used for RECIST assessment are summarised in Table 1 and those excluded for tumour assessments in this study are discussed below, with the rationale provided.

Target Lesions	Non target lesions	New Lesions
CT (preferred)	CT (preferred)	CT (preferred)
MRI	MRI	MRI
	Clinical examination	Clinical examination
	X-ray, chest X-ray	X-ray, chest X-ray
		Ultrasound
		Bone scan
		FDG-PET

Table 1Summary of Methods of Assessment

3.1 CT and MRI

CT and MRI are generally considered to be the best currently available and reproducible methods to measure TLs selected for response assessment and to assess NTLs and identification of new lesions.

In this study it is recommended that CT examinations of the chest and abdomen will be used to assess tumour burden at baseline and follow-up visits. CT examination with intravenous contrast media administration is the preferred method. MRI should be used where CT is not feasible or it is medically contra-indicated. For assessment of brain lesions MRI is the preferred method.

3.2 Clinical examination

Clinical examination will not be used for assessment of TLs. Clinically detected lesions can be selected as TLs if they are then assessed by CT or MRI scans. Clinical examination can be used to assess NTLs in patients that also have other lesions assessable by CT, MRI or plain Xray and to identify the presence of new lesions.

3.3 X-rays

3.3.1 Plain X-ray

Plain X-rays may be used as a method of assessment for bone NTLs and to identify the presence of new bone lesions.

3.3.2 Chest X-ray

Chest X-rays will not be used for assessment of TLs as they will be assessed by CT or MRI examination. Chest X-rays can, however, be used to assess NTLs and to identify the presence of new lesions.

3.4 Ultrasound

Ultrasound examination will not be used for assessment of TLs and NTLs as it is not a reproducible method, does not provide an accurate assessment of tumour size and it is subjective and operator dependent. Ultrasound examination can, however, be used to identify the presence of new lesions. If new clinical symptoms occur and an ultrasound is performed then new lesions should be confirmed by CT or MRI examination.

3.5 Endoscopy and laparoscopy

Endoscopy and laparoscopy will not be used for tumour assessments as they are not validated in the context of tumour measurements.

3.6 Tumour markers

Tumour markers will not be used for tumour response assessments per RECIST 1.1.

3.7 Cytology and histology

Histology will not be used as part of the tumour response assessment per RECIST 1.1.

Cytological confirmation of the neoplastic origin of any effusion that appears or worsens during treatment is required when the measurable tumour has met criteria for response or stable disease. In such circumstances, the cytology is necessary to differentiate between response / stable disease (an effusion may be a side effect of the treatment) and progressive disease (if the neoplastic origin of the fluid is confirmed). Where cytology findings are not available, any effusion that significantly worsens (from trace to large) or the appearance of a clinically significant effusion (requiring change in drug therapy) during the study treatment will be considered to be progression of NTLs or disease progression due to new lesions.

3.8 Isotopic bone scan

Bone lesions identified on an isotopic bone scan at baseline and confirmed by CT, MRI or X-ray at baseline should be recorded as NTLs and followed by the same method as per baseline assessment.

Isotopic bone scans may be used as a method of assessment to identify the presence of new bone lesions at follow-up visits. New lesions will be recorded where a positive hot-spot that was not present on the baseline bone scan assessment is identified on a bone scan performed at any time during the study. The Investigator should consider the positive hot-spot to be a significant new site of malignant disease and represent true disease progression in order to record the new lesion. Confirmation by CT, MRI and x-ray is recommended where bone scan findings are equivocal.

3.9 FDG-PET scan

FDG-PET (fluorodeoxyglucose positron emission tomography) scans may be used as a method for identifying new lesions, according with the following algorithm: New lesions will be recorded where there is positive FDG uptake (defined as when an uptake greater than twice that of the surrounding tissue is observed) not present on baseline FDG-PET scan or in a location corresponding to a new lesion on CT/MRI at the same follow-up visit. If there is no baseline FDG-PET scan available, and no evidence of new lesions on CT/MRI scans then follow-up CT/MRI assessments should be continued, scheduled as per protocol or clinical indicated, in order to confirm new lesions.

4. TUMOUR RESPONSE EVALUATION

4.1 Schedule of evaluation

CT examinations of the chest and abdomen (including liver adrenal glands) will be used to assess tumour burden at baseline and follow-up visits. CT examination with intravenous contract media administration is the preferred method. MRI should be used where CT is no feasible or it is medically contra-indicated.

Clinical Study Protocol Appendix F Drug Substance AZD9291 Study Code D5160C00001 Edition Number 1 Date

Baseline tumour assessments should encompass all areas of known predilection for metastases in the disease under evaluation and should additionally investigate areas that may be involved based on signs and symptoms of individual patients and should be performed no more than 28 days before the start of study treatment. Follow-up assessments should be performed every 6 weeks (\pm 7 days) after the start of treatment until discontinuation of study treatment or withdrawal of consent. Any other sites at which new disease is suspected should also be adequately imaged at follow-up.

If an unscheduled assessment was performed and the patient has not progressed, every attempt should be made to perform the subsequent assessments as their scheduled visits. This schedule is to be followed in order to minimise any unintentional bias caused by some patients being assessed at different frequency than other patients.

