5.1.6.1 Escalation and expansion patients

[figure not shown]
If any other toxicity resolves or reverts to \leq CTCAE grade 2 within 21 days of onset and the patient is showing clinical benefit, treatment with AZD9291 may be restarted at the same dose or a lower dose using the rules below for dose modifications (see Figure 2) and agreement with the AstraZeneca Study Team Physician as needed.

[figure not shown]
If any other toxicity does not resolve to \leq CTCAE grade 2 after 21 days, then the patient should be withdrawn from the study and observed until resolution of the toxicity

On resolution of toxicity within 21 days:

- If a further episode of the same AE subsequently requires dose interruption, AZD9291 must restart at one dose level lower (unless in Cohort 1, when restart will be at Cohort 1 dose) on improvement of the AE.
- If a different AE subsequently requires dose interruption, AZD9291 may restart at the same or one dose level lower (unless in Cohort 1, when restart will be at Cohort 1 dose) on improvement of the AE at the discretion of the Investigator.

Patients who are at the lowest possible dose ie, who have their dose previously reduced to the Cohort 1 dose and who have demonstrated an acceptable response to the dose interruption may be permitted to restart at the lowest dose level at the discretion of the Investigator.

5.1.6.2 Phase II extension patients:

If any other toxicity resolves or reverts to \leq CTCAE grade 2 within 21 days of onset, treatment with AZD9291 may be restarted at the same dose (80 mg) or a lower dose (40 mg) following discussion and agreement with the AstraZeneca Study Team Physician as needed. There will be no individual modifications to dosing schedule in response to toxicity, only potential dose

reduction or dose interruption. If the toxicity does not resolve to \leq CTCAE grade 2 after 3 weeks, then the patient should be withdrawn from the study and observed until resolution of the toxicity.

On resolution of toxicity within 3 weeks:

• If an AE subsequently requires dose interruption, AZD9291 may restart at the same dose or the reduced dose, on resolution/improvement of the AE at the discretion of the Investigator.

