5.1.7 Duration of therapy

Patients should continue on treatment with AZD9291 until RECIST 1.1 defined progression or until treatment discontinuation criteria is met. There is no maximum duration of treatment as patients may continue to receive AZD9291 beyond RECIST 1.1 defined progression as long as they are continuing to show clinical benefit, as judged by the investigator.

If AZD9291 is discontinued for reasons other than disease progression, the patient must continue RECIST 1.1 assessments every 6 weeks until disease progression, even if further lines of anticancer therapy are administered.

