5.4.1 Procedures for discontinuation of a patient from investigational product

Once study medication is permanently discontinued it cannot be restarted.

A patient who discontinues study treatment is not always automatically withdrawn from the study. If a patient is withdrawn from study, see Section 5.4.3

Any patients who discontinue study treatment for reasons other than objective disease progression should have tumour assessments scans performed as scheduled in the protocol (see Table 2, Table 3 and Table 4 until objective disease progression is documented or death occurs, unless consent is withdrawn. Study procedure related SAEs and concomitant medication must be captured until the patient no longer has RECIST 1.1 assessments (disease progression or permanent withdrawal from the study).

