6.3.8.2 Progression follow-up

Patients who discontinue AZD9291 for reasons other than progression will continue RECIST 1.1 assessments every 6 weeks (relative to first dose of multiple dosing). Details of concomitant medications (including any subsequent cancer therapy) should continue to be collected as detailed in the study plan (see Table 2, Table 3 and Table 4) up to the 28-day follow up visit. Only new SAEs due to study procedures should be collected. For those patients in the expansion cohorts an additional PRO QoL questionnaire should be completed on progression (Table 3). Beyond the 28-day follow up visit only subsequent cancer therapy should be collected.

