6.10 Anti-tumour activity

6.10.1 Tumour assessments

RECIST 1.1 guidelines for measurable, non-measurable, target lesions (TLs) and non-target lesions (NTLs) and the objective tumour response criteria are presented in Appendix F of this Clinical Study Protocol.

Baseline CT or MRI assessments of chest and abdomen (including liver and adrenal glands) must be performed no more than 28 days before the start of study treatment, and ideally

should be performed as close as possible to the start of study treatment. Additional imaging may be performed based on individual patient signs and symptoms. CT/MRI scan of the brain should be performed in patients with known or suspected brain mestastases.

The methods of assessment used at baseline should be used at each subsequent follow-up assessment. Follow-up assessments should be performed every 6 weeks (\pm 7 days) after the start of multiple dosing until objective disease progression as defined by RECIST 1.1 even if a patient discontinues treatment prior to progression.

Any other sites at which new disease is suspected should also be appropriately imaged. If an unscheduled assessment is performed and the patient has not progressed, every attempt should be made to perform subsequent assessments at the scheduled visits whilst the patient remains on study treatment.

Categorisation of objective tumour response assessment will be based on the RECIST 1.1 guidelines for response: CR (complete response), PR (partial response), SD (stable disease) and PD (progression of disease). Target lesion progression will be calculated in comparison to when the tumour burden was at a minimum (i.e. smallest sum of diameters previously recorded on study). In the absence of progression, tumour response (CR, PR, SD) will be calculated in comparison to the baseline tumour measurements obtained before starting treatment.

If the investigator is in doubt as to whether progression has occurred, particularly with response to NTLs or the appearance of a new lesion, it is advisable to continue treatment and reassess the patient's status at the next scheduled assessment or sooner if clinically indicated. If repeated scans confirm progression, then the date of the initial scan should be declared as the date of progression.

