4.5 Symptomatic deterioration

Symptomatic deterioration is not a descriptor of an objective response: it is a reason for stopping study therapy.

Patients with 'symptomatic deterioration' requiring discontinuation of study treatment without objective evidence of disease progression at that time should continue to undergo RECIST 1.1 assessments according to the clinical study protocol until objective disease progression is observed.

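### Appendix F Section 4.1 ends RECIST scans when study treatment stops, contradicting the scan-until-progression rule that PFS and DoR rely on

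*Protocol*

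**What the plan says.** Appendix F Section 4.1 (Schedule of evaluation) runs follow-up scans every 6 weeks "after the start of treatment until discontinuation of study treatment or withdrawal of consent". Progression is not mentioned as an end point. Section 6.10.1 stresses keeping to the schedule and points the reader to two places for it: the study plan in 6.1 and Appendix F Section 4.1.

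Elsewhere the rule is different:

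- Section 5.1.7, after stopping for reasons other than progression: "the patient must continue RECIST 1.1 assessments every 6 weeks until disease progression, even if further lines of anticancer therapy are administered".
- Section 5.4.1: scans as scheduled "until objective disease progression is documented or death occurs, unless consent is withdrawn".
- Section 6.3.8.2: "Patients who discontinue AZD9291 for reasons other than progression will continue RECIST 1.1 assessments every 6 weeks".
- Section 6.10.1: "until objective disease progression as defined by RECIST 1.1 even if a patient discontinues treatment prior to progression".
- Tables 2 to 4: RECIST every 6 weeks until progression.
- Appendix F Section 4.5: patients stopped for symptomatic deterioration "should continue to undergo RECIST 1.1 assessments according to the clinical study protocol until objective disease progression is observed".

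Section 7.7.2 defines PFS so that stopping AZD9291 or starting another anticancer therapy does not end follow-up, and it censors patients without an event at their last evaluable RECIST assessment. Section 7.7.3 takes the end or censoring date of DoR from PFS.

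Sections 5.1.6.1 and 5.1.6.2 say that if toxicity does not resolve in the stated time, "then the patient should be withdrawn from the study and observed until resolution of the toxicity". The QTc rule in the opening text of 5.1.6 withdraws the patient from study treatment only.

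**The concern.** The protocol gives two incompatible instructions on when scanning ends, and the outlying one sits in the RECIST guide to which the main text sends the reader. A site working from Appendix F Section 4.1 would stop imaging a patient who comes off drug for toxicity while still progression-free.

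That patient would then be censored for PFS, and for DoR if a responder, at the last on-treatment scan. If a later death is captured, the event would instead be dated at death rather than at the earlier, unseen progression. The result would be close to a PFS censored at treatment stop, which is not the quantity defined in 7.7.2. If patients who stop early tend to progress sooner than those who stay on drug, the censoring is informative and PFS and DoR look longer than they are. Scans that were not done cannot be recovered at analysis.

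**Working it through.** **Comparing the texts.** No stated figure is in dispute, so the main check is a side-by-side reading.

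| Place | End of scanning after a stop without progression |
|---|---|
| Appendix F 4.1 | At the stop, or at withdrawal of consent |
| 5.1.7 | Progression, even on new therapy |
| 5.4.1 | Progression or death, unless consent is withdrawn |
| 6.3.8.2 | Not at the stop: 6-weekly scans continue |
| 6.10.1 | Progression |
| Tables 2 to 4 | Progression |
| Appendix F 4.5 (symptomatic deterioration) | Progression |
| 7.7.2 and 7.7.3 (PFS, DoR) | Need scans to progression |

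Appendix F Section 4.1 stands alone, and the conflict is direct. Because Appendix F Section 4.5 separately protects symptomatic deterioration, the patients exposed are those who stop before progression for other reasons, such as toxicity.

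**The toxicity wording.** Section 5.1.7 requires scans after any stop that is not for progression. Sections 5.1.6.1 and 5.1.6.2 withdraw the patient from the study. Section 5.4.1 lists permanent withdrawal from the study among the ways RECIST assessments end, and 5.4.3 describes leaving the study as covering both drug and assessments. Read through those two sections, 5.1.6.1 and 5.1.6.2 conflict with 5.1.7, but only by implication.

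**Illustrative size.** The protocol gives no rate of stopping without progression and no hazard afterwards, so every input here is an assumption:

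- On-treatment PFS is exponential with median 10 months: λ = ln 2 / 10 = 0.0693 per month.
- A proportion p of 10% or 20% stops before progression: stopping hazard δ = λp/(1 − p), which is 0.0077 or 0.0173.
- The hazard after stopping is hλ, with h from 1 to 3.
- Every patient who stops loses all later scans, and no later death is counted.

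True PFS is S(t) = e^(−(λ+δ)t) + [δ/(hλ − λ − δ)] × [e^(−(λ+δ)t) − e^(−hλt)].

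Censoring at the stop estimates e^(−λt) instead: median 10.0 months and 12-month PFS 0.5^1.2 = 43.5%.

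Worked case, p = 20% and h = 2: δ/(hλ − λ − δ) = 0.0173/0.0520 = 1/3. So S(12) = (4/3)(0.3536) − (1/3)(0.1895) = 0.4714 − 0.0632 = 40.8%.

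| p | h | True median (months) | True 12-month PFS |
|---|---|---|---|
| 10% or 20% | 1 | 10.0 | 43.5% |
| 10% | 1.5 | 9.84 | 42.8% |
| 20% | 1.5 | 9.65 | 42.0% |
| 10% | 2 | 9.71 | 42.3% |
| 20% | 2 | 9.40 | 40.8% |
| 10% | 3 | 9.53 | 41.5% |
| 20% | 3 | 9.05 | 39.2% |

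The overstatement is therefore 0 to about 0.9 months in the median and 0 to about 4 points at 12 months. For scale, the 95% half-width for a 12-month PFS of 43.5% in 175 patients with no earlier censoring is 1.96 × √(0.435 × 0.565/175) = 7.3 points. DoR was not computed.

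**The case against.** The intent is not in real doubt. Section 5.1.7 says the patient must continue scans, several other sections and all three study plan tables agree, and 6.10.1 cites the study plan alongside Appendix F Section 4.1. Many sites would do the right thing. PFS and DoR are secondary, single-arm and descriptive; the extension's primary endpoint is ORR. The illustration rests on no protocol figure, shows no bias at a hazard ratio of 1, and supposes that every affected patient loses every later scan. All of this stands. It limits the consequence without removing the contradiction.

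Four stronger readings are tempting, and the documents do not support them:

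- *Patients with symptomatic deterioration are lost.* Appendix F Section 4.5 keeps them on scans until objective progression.
- *Overall survival follow-up in the extension is lost.* Section 6.3.8.3 requires 6-weekly survival contact after progression, and its only exception is withdrawal of consent. A toxicity stop is not an exception, so loss of OS data does not follow.
- *The toxicity sections plainly end RECIST follow-up.* Section 5.4.3 deals with a patient's own withdrawal of consent, and 5.1.6.1 and 5.1.6.2 keep the patient under observation until the toxicity resolves. The parenthesis in 5.4.1 gives some support, so the wording is ambiguous and no more.
- *PFS is materially inflated.* The direction depends on earlier progression after stopping, and the size cannot be derived from the protocol.

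**Conclusion.** Appendix F Section 4.1 is wrong as written. It contradicts the main text, the study plan and its own Section 4.5, and it cannot deliver the PFS and DoR that 7.7.2 and 7.7.3 define. Where it is followed, patients who stop before progression for reasons other than symptomatic deterioration lose scans that cannot be replaced. PFS and DoR would then be overestimated if those patients progress sooner than others.

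The size is unknown. With an assumed 10-month median, 10 to 20% stopping early and a hazard ratio of 1 to 3 afterwards, a reported median of 10.0 months would correspond to a true one of about 9.1 to 10.0. That is a modest shift in secondary endpoints, and it is illustrative only. The wording in 5.1.6.1 and 5.1.6.2 is a secondary matter of clarification.

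**What to change.** In Appendix F Section 4.1, replace the stop rule so that scans run *until objective progression by RECIST 1.1, even if study treatment is discontinued, unless consent is withdrawn*. That matches 6.10.1 and 5.4.1.

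As a secondary clarification, reconcile the study-withdrawal wording in 5.1.6.1 and 5.1.6.2 with the treatment-only wording in 5.1.6 and with 5.1.7, 5.4.1 and 6.3.8. State that RECIST follow-up, and survival follow-up where it applies, continue after such a stop. The toxicity rule itself is not changed.

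The cost is wording only. The main text already requires these scans, so no procedure is added.
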